12.1.2. Attribution Definitions

Not Related

An adverse event that is not related to the use of the drug.

Doubtful

An adverse event for which an alternative explanation is more likely, eg, concomitant drug(s), concomitant disease(s), or the relationship in time suggests that a causal relationship is unlikely.

Possible

An adverse event that might be due to the use of the drug. An alternative explanation, eg, concomitant drug(s), concomitant disease(s), is inconclusive. The relationship in time is reasonable; therefore, the causal relationship cannot be excluded.

Probable

An adverse event that might be due to the use of the drug. The relationship in time is suggestive (eg, confirmed by dechallenge). An alternative explanation is less likely, eg, concomitant drug(s), concomitant disease(s).

Very Likely

An adverse event that is listed as a possible adverse reaction and cannot be reasonably explained by an alternative explanation, eg, concomitant drug(s), concomitant disease(s). The relationship in time is very suggestive (eg, it is confirmed by dechallenge and rechallenge).

12.1.3. Severity Criteria

The severity assessment for an adverse event or serious adverse event should be completed using the NCI-CTCAE Version 4.03. Any adverse event or serious adverse event not listed in this document will be graded according to investigator clinical judgment by using the standard grading outlined in the NCI-CTCAE Version 4.03.

The investigator should use clinical judgment in assessing the severity of events not directly experienced by the subject (eg, laboratory abnormalities).

12.2. Special Reporting Situations

Safety events of interest on a sponsor study drug that may require expedited reporting and/or safety evaluation include, but are not limited to:

- Overdose of a sponsor study drug. No MTD has been reached for daratumumab. However, if the dose exceeds the maximum tested dose of 24 mg/kg, then it will be considered as overdose in this study.
- Suspected abuse/misuse of a sponsor study drug
- Inadvertent or accidental exposure to a sponsor study drug
- Medication error involving a sponsor product (with or without subject exposure to the sponsor study drug, eg, name confusion)

Special reporting situations should be recorded in the eCRF. Any special reporting situation that meets the criteria of a serious adverse event should be recorded on the adverse event page of the eCRF.

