An Independent Data Monitoring Committee (IDMC) will be commissioned for this study to review efficacy and safety results at the planned interim analyses. After the interim review, they will make recommendations regarding the continuation of the study. In addition, the IDMC may also review cumulative safety data every 6 months besides the 2 interim analyses. The IDMC will no longer review study data after the interim PFS analysis has been completed.

Assessment of tumor response and disease progression will be conducted in accordance with the International Myeloma Working Group (IMWG) response criteria. An assessment of MRD will be conducted on bone marrow samples. Safety evaluations will include adverse event monitoring, physical examinations, electrocardiogram (ECG) monitoring, clinical laboratory parameters (hematology and chemistry), vital sign measurements, and Eastern Cooperative Oncology Group (ECOG) performance status. Blood samples will be drawn for assessment of pharmacokinetic parameters.

Following the positive second interim analysis that established the superiority of DRd over Rd alone with respect to the primary endpoint (PFS), the sponsor will provide access to daratumumab for subjects randomized to Arm A (Rd) who have sponsor-confirmed disease progression (see Section 8.4, Subsequent Therapies), if recommended by the investigator. After the cut-off for the final CSR, sponsor confirmation of PD is no longer required and will be based on investigator assessment of PD.

SUBJECT POPULATION

Key eligibility criteria include the following: subjects who are ≥18 years of age, have a confirmed diagnosis of symptomatic multiple myeloma and measurable secretory disease, an ECOG performance status score of 0, 1, or 2, must be newly diagnosed and not considered candidates for high-dose chemotherapy with stem cell transplantation (SCT).

DOSAGE AND ADMINISTRATION

Daratumumab IV (16 mg/kg) or daratumumab SC (1800 mg fixed dose) will be administered to subjects assigned to Arm B initially once every week for 8 weeks; then once every other week for 16 weeks; thereafter once every 4 weeks until documented progression, unacceptable toxicity, or study end.

Lenalidomide will be self-administered at a dose of 25 mg PO each day on Days 1 through 21 of each 28-day cycle.

Dexamethasone (or equivalent in accordance with local standards; see Attachment 6 for conversion table) will be administered at a total dose of 40 mg weekly.

EFFICACY EVALUATIONS/ENDPOINTS

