1.2.2. Clinical Studies

1.2.2.1. Single-Agent Daratumumab Studies (GEN501 and MMY2002)

Two single-agent studies with daratumumab are ongoing (Studies GEN501 and MMY2002), as described in Table 1.

Table 1: Daratumumab Single-Agent Studies GEN501 and MMY2002

Study Number	Study Design	Number of sul	bjects Treated/	
	, s			
GEN501	Open label, Phase 1/2, first in human, single agent study in subjects with multiple myeloma whose disease is relapsed or refractory to at least 2 prior lines of therapies Population was heavily treated with prior treatment, including ASCT, chemotherapy based regimens, IMiDs, and PIs	Treatment Regimen Part 1 n 32 total treated with daratumumab weekly 0.005 1 mg/kg (n 17) 2 mg/kg (n 3) 4 mg/kg (n 3) 8 mg/kg (n 3) 16 mg/kg (n 3) 24 mg/kg (n 3) Part 2 n 51 total treated 8 mg/kg (n 30) Weekly for 8 weeks, followed by q2w for an additional 16 weeks, and monthly thereafter First dose, followed by weekly defor 7 weeks, then q2w for a additional 14 weeks, a monthly thereafter		
MMY2002	Open label, multicenter, 2 stage, Phase	n 34 total treated in Stage 1		
ACCT and large	2 study of daratumumab for the treatment of subjects with multiple myeloma who have received at least 3 prior lines of therapy including a PI and an IMiD or whose disease is double refractory to both a PI and an IMiD	8 mg/kg (n 18) q4w	16 mg/kg (n 16) qw for 8 weeks, then q2w for another 16 weeks, and then q4w thereafter	

ASCT autologous stem cell transplantation; IMiD immunomodulatory agent; PI proteasome inhibitor; q2w every 2 weeks; q4w every 4 weeks

Among the 32 subjects treated in Part 1 of Study GEN501, the maximum tolerated dose (MTD) was not reached following intravenous (IV) infusions up to 24 mg/kg. Two subjects experienced dose-limiting toxicities (DLTs) in the lower dose cohorts (a subject in the 0.1-mg/kg group had Grade 3 anemia and Grade 4 thrombocytopenia, and a subject in the 1.0-mg/kg group had Grade 3 aspartate aminotransferase increased).

Among the 51 subjects treated in Part 2 of Study GEN501, serious adverse events (SAEs) were reported in 37% of subjects (43% of subjects in the 8-mg/kg group and 29% of subjects in the 16 mg/kg-group). The most frequently reported SAEs were pneumonia (6% subjects), and pyrexia (4% of subjects).

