All subjects randomized to Treatment Arm B in this study initially received daratumumab IV formulation; however, following implementation of protocol amendment 8, subjects still receiving treatment with daratumumab IV will have the option to switch to daratumumab SC on Day 1 of any cycle, at the discretion of the investigator. Subjects with a known allergy/intolerance to sorbitol will not be eligible to switch to daratumumab SC. Note: throughout this document, text has been added to highlight any differences between daratumumab IV and daratumumab SC dosing, and where there is no clarification, it is implied that the descriptions are the same for daratumumab IV and daratumumab SC.

The Follow-up Phase will begin once a subject discontinues all study treatments. Subjects who discontinue study treatment for reasons other than disease progression must continue to have disease evaluations according to the Time and Events Schedule until confirmed disease progression (PD) (see Section 8.4, Subsequent Therapies). After PD is documented, follow-up will be obtained at least every 16 weeks. Subsequent anti-myeloma therapy, PFS2 (per investigator judgment), second primary malignancies, and survival will be recorded. The Follow-up Phase will continue until death, lost to follow up, consent withdrawal, or study end, whichever occurs first.

Two interim analyses are planned. The first interim analysis, with a purpose to evaluate safety, will be performed after a total of approximately 100 subjects have been treated for at least 8 weeks or discontinued the study treatment. The second interim analysis will be performed when 234 PFS events, which is 60% of the total planned events, have been accumulated. The purpose of this interim analysis is to evaluate cumulative interim safety and efficacy data. The significance level at this interim analysis to establish the superiority of DRd over Rd with regard to PFS will be determined based on the observed number of PFS events at the interim analysis, using the O'Brien-Fleming boundaries as implemented by the Lan-DeMets alpha spending method. If the experimental arm (DRd) is numerically worse than the control arm in terms of PFS (observed hazard ratio >1 favoring the control arm), then the study may be terminated for futility.

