In MMY1004, the 1800 mg dose achieved maximum C_{trough} (Cycle 3 Day 1 predose) values that were similar or greater than the maximum C_{trough} observed for the approved 16 mg/kg IV dose following the same dose schedule. The PK data from Part 2 supported the daratumumab SC 1800 mg dose selection for the Phase 3 study. The PK data from MMY3012 study demonstrated that daratumumab SC 1800 mg is non-inferior to daratumumab IV 16 mg/kg in terms of maximum C_{trough} (Cycle 3 Day 1 predose), with the lower bound of the 90% CI for the geometric means ratio for daratumumab SC versus daratumumab IV for maximum C_{trough} (Cycle 3 Day 1 predose) exceeding 80%, thereby meeting the predefined non-inferiority criterion.

Additionally, daratumumab SC 1800 mg monotherapy consistently produced lower peak-to-trough fluctuations, similar or slightly higher trough levels over time, and lower peak concentrations compared with daratumumab IV 16 mg/kg monotherapy. Overall, consistent daratumumab concentrations were observed across the body weight ranges. As expected, slightly higher concentrations were observed for subjects with lower body weights.

There was no apparent relationship between exposure and safety endpoints (SAEs, Grade 3 or higher treatment-emergent adverse events and neutropenia).

Overall, daratumumab SC was well-tolerated with manageable side effects and a significantly reduced incidence of IRRs relative to daratumumab IV. The safety profile of daratumumab administered subcutaneously at a flat dose of 1800 mg continued to be generally comparable to that of the 16 mg/kg IV formulation.

Rationale for DNA and Biomarker Collection

Biomarker samples will be collected to evaluate the depth of clinical response to daratumumab through evaluation of MRD, using DNA sequencing of immunoglobulin genes, and to determine response rates in specific molecular subgroups of multiple myeloma, using DNA/RNA sequencing of multiple myeloma cells to allow for assessment of high risk genomics such as deletion 17p, t(4;14), t(14;20), t(14;16), deletion13, GEP signatures such as UAMS-70, and mutations in p53, BRAF, FGFR, IGH, PI3K, or other molecular subtypes associated with disease progression. Other biomarker goals include evaluation of potential mechanisms of resistance, inter-individual variability in clinical outcomes or identification of population subgroups that respond differently to treatment.

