6. DOSAGE AND ADMINISTRATION

In this protocol, the term "study drug" refers to daratumumab only (daratumumab IV or daratumumab SC), and "study treatment" refers to daratumumab, lenalidomide, and dexamethasone. Daratumumab is to be administered as described in the Time and Events Schedule. Each cycle is 28 days. The first visit of a cycle should be 4 weeks after the start of the previous cycle. The start of each cycle may occur ±3 days of the scheduled day in order to accommodate the schedule of the site or subject. Day 1 of subsequent cycles should be adjusted accordingly to maintain the 28-day cycle duration. In Cycles 1 through 6, weekly or bi-weekly daratumumab doses may be given within ±1 day of the scheduled day in order to accommodate the schedule of the site or subject. In all cycles, weekly dexamethasone doses may be given within ±1 day of the scheduled day in order to accommodate the schedule of the site or subject. Changes to within-cycle dosing should not impact Day 1 of the next cycle. Subjects will continue to receive study treatment according to the Time and Events Schedule until disease progression, unacceptable toxicity, or other reasons as listed in Section 10.2.

Subjects whose study treatment is delayed for more than 4 weeks (Cycle 1 to Cycle 6) or more than 6 weeks (Cycle 7 and beyond) should have study treatment discontinued, unless, upon consultation with the sponsor and the review of safety and efficacy, continuation is agreed upon.

A schematic of study treatment administration is provided in Figure 4.

[figure not shown]

Figure 4: Schematic Overview Study Treatment Administration

 On days when daratumumab is administered, dexamethasone will be administered to subjects in Arm B in the clinic and will serve as the treatment dose of steroid as well as the required pre-medication prior to daratumumab infusion.

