6.1.2. Daratumumab IV Administration

Daratumumab (16 mg/kg) will be administered by IV infusion to subjects in Arm B initially once every week for 8 weeks; then once every other week for 16 weeks; thereafter once every 4 weeks until documented progression, unacceptable toxicity, or study end (as defined in Section 17.9.1).

Each subject's dose will be calculated based on the subject's weight rounded to the nearest kilogram. There is no cap on the absolute dose allowed, as long as the dose does not exceed 16 mg/kg. If a subject's weight changes by more than 10% from baseline, the dose of daratumumab will be re-calculated. For recommendations on daratumumab infusion rate, please refer to the SIPPM. All infusions will be performed as outpatient visits. Subjects will receive preinfusion medications and postinfusion medications as outlined in Section 6.1.4.

Every effort should be made to keep subjects on the planned dosing schedule. Time windows for daratumumab administration are outlined in Table 3.

As noted in the Time and Events Schedule, vital signs should be monitored extensively on Cycle 1 Day 1 before, during, and after the first infusion of daratumumab. For all other infusions, vital signs should be measured before the start of infusion and at the end of the infusion. If a subject experiences any significant medical event, then the investigator should assess whether the subject should stay overnight for observation.

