6.1.3. Daratumumab SC Administration

Daratumumab SC will be administered by SC injection at a fixed dose of 1800 mg once every 4 weeks until documented progression, unacceptable toxicity, or study end (as defined in Section 17.9.1). Doses will be administered by manual push over 3-5 minutes in the abdominal SC tissue, rotating between the four quadrants. The volume of the SC solution will be 15 mL for the 1800 mg dose. Refer to the Investigational Product Preparation Instructions (IPPI) for additional guidance on SC administration of daratumumab SC.

The dose of daratumumab will remain constant throughout the study. For subjects who initially received daratumumab IV and then switch to daratumumab SC following Amendment 8, it is recommended subjects are observed for a period of time deemed appropriate by the investigator following the first daratumumab SC dose and, if necessary, after subsequent injections. Reasons for continued observation on subsequent daratumumab administrations may include but are not limited to the following: subjects with a higher risk of respiratory complications (eg, subjects with mild asthma or subjects with COPD who have an FEV1 <80% at screening or developed FEV1 <80% during the study without any medical history), subjects with IRR with prior administrations of study drug, subject with a decreased condition on day of dosing compared to prior dosing day.

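### The Section 12.2 overdose limit of 24 mg/kg comes from IV dosing; as written, it makes a correct 1800 mg SC dose an overdose in any switched subject under 75 kg

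*Protocol*

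**What the plan says.** Protocol Section 12.2 (Special Reporting Situations) lists overdose of a sponsor study drug as a safety event of interest. It notes that no maximum tolerated dose has been reached and continues: "if the dose exceeds the maximum tested dose of 24 mg/kg, then it will be considered as overdose in this study". No route is named and no separate SC limit is given.

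Five other parts of the protocol bear on how that sentence reads:

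- **Origin of the figure.** Section 1.2.2.1 reports that in Study GEN501 Part 1 the maximum tolerated dose "was not reached following intravenous (IV) infusions up to 24 mg/kg".
- **SC dose.** Section 6.1.3: "Daratumumab SC will be administered by SC injection at a fixed dose of 1800 mg once every 4 weeks". The dose stays constant and is not scaled to weight.
- **Meaning of study drug.** Section 6 says the term "refers to daratumumab only (daratumumab IV or daratumumab SC".
- **Default reading.** Section 3.1 (and the Synopsis) says that "where there is no clarification, it is implied that the descriptions are the same for daratumumab IV and daratumumab SC".
- **Units by route.** The Synopsis, under Dosage and Administration, gives each route its own unit: "Daratumumab IV (16 mg/kg) or daratumumab SC (1800 mg fixed dose".

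Section 12.2 says special reporting situations should be recorded in the eCRF. Section 12.3.1 requires them to be reported until long-term survival follow-up starts.

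**The concern.** A limit in mg/kg suits a weight-based IV dose. Applied to a fixed SC dose, it turns into a limit on body weight: light subjects cross it when dosed exactly as the protocol requires, and heavier subjects do not.

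The protocol's own reading rules lead to this result. The overdose bullet covers the study drug, which includes both routes, and the text does not separate the routes, so Section 3.1 applies it to both. Nothing in either document exempts SC. The Amendment 8 change log does not list Section 12.2 among the sections adapted for SC. That is only supporting evidence; the conflict is in the current text.

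Two things are at stake:

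- A site following the wording would record every correct SC dose in a lighter subject as an overdose. A site assuming the limit is for IV only would record none. The overdose records would then not be comparable between sites.
- Below the crossover weight, the definition cannot tell a correct SC dose from a real SC dosing error.

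**Working it through.** **Inputs**

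- Overdose limit: more than 24 mg/kg (Section 12.2).
- SC dose: 1800 mg fixed (Section 6.1.3).
- SC volume 15 mL (Section 6.1.3) and concentration 120 mg/mL (Sections 14.1 and 14.2).
- IV dose: 16 mg/kg, not to be exceeded (Section 6.1.2).
- Weight margin for IV dose recalculation: 10% (Section 6.1.2).

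**1. Reproduce the stated SC dose.** 15 mL × 120 mg/mL = 1800 mg, as stated.

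**2. Crossover weight.** Fixed dose / limit = 1800 mg / 24 mg/kg = 75 kg.

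**3. SC dose per kg at illustrative weights (1800 / weight)**

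| Weight (kg) | mg/kg | Above 24? |
|---|---|---|
| 50 | 36.0 | yes |
| 60 | 30.0 | yes |
| 70 | 25.7 | yes |
| 74 | 24.3 | yes |
| 75 | 24.0 | no (equal to the limit) |
| 80 | 22.5 | no |
| 90 | 20.0 | no |

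A correct IV dose of 16 mg/kg never crosses the limit, so the problem belongs to SC alone.

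**4. Which weight?** Section 12.2 does not say whether baseline or current weight is used. Section 6.1.2 provides a margin for IV: if a subject's "weight changes by more than 10% from baseline, the dose of daratumumab will be re-calculated". Assume, for illustration, that current weight is within that 10% of baseline:

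- Baseline below 75 / 1.1 = 68.2 kg: overdose on either weight.
- Baseline of 75 / 0.9 = 83.3 kg or more: not an overdose on either weight.
- In between: the classification depends on which weight is used.

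**5. Does the protocol regard 1800 mg as excessive in lighter subjects?** No. Section 3.2 reports that "consistent daratumumab concentrations were observed across the body weight ranges". It adds that lighter subjects had slightly higher concentrations, as expected, and describes SC safety as generally comparable to IV. The protocol therefore supports the dose at weights where Section 12.2 calls it an overdose.

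**The case against.** The strongest reply is that the limit was plainly meant for IV. It is tied to the maximum tested dose, which is an IV finding, and the protocol uses mg/kg for IV and fixed mg for SC. Moreover, 1800 mg SC is itself a tested dose: Section 1.2.2.3 describes a Phase 3 study with 263 subjects assigned to it. On that view a correct SC dose does not exceed any tested dose, and the text is ambiguous rather than wrong. The default rule in Section 3.1 can also misfire elsewhere. The Time and Events dose administration table has all study treatments recalculated after a 10% weight change, while Section 6.1.3 keeps the SC dose constant.

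This is persuasive about intent, but no text limits the threshold to IV. The bullet states 24 mg/kg as the number that defines overdose, under a term defined to include SC.

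Several points about scale do stand:

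- Section 12.2 says such events may require expedited reporting, so no expedited report follows automatically.
- Routine reporting of special situations stops when long-term survival follow-up begins, and the CRF pages kept open in Attachment 11 include none for them. A later amendment might take effect after that window has closed.
- Sites also had the Investigator's Brochure, the product preparation instructions and the eCRF guidelines. These are not available here and may or may not address SC overdose.
- The 10% margin in step 4 is borrowed from IV dosing; Section 12.2 does not use it.

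**Conclusion.** The concern holds. Followed as written, Section 12.2 classifies a correct 1800 mg SC dose as an overdose in any switched subject under 75 kg. This is a stated threshold that gives the wrong answer for one route, not merely missing detail.

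The consequence is modest: it affects safety classification and reporting only, up to the start of long-term survival follow-up. Dosing, efficacy results and the planned SAP outputs do not change, and nothing here suggests harm to subjects.

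The 75 kg figure needs no assumption beyond the two doses in the protocol; the 68.2 to 83.3 kg range rests on the 10% weight assumption. No count of affected subjects is claimed, and the documents do not show how sites applied the rule.

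**What to change.** In the Section 12.2 overdose bullet, restrict the 24 mg/kg limit to daratumumab IV and add a separate SC limit as an absolute dose in mg, no lower than 1800 mg. The sponsor's safety team should choose the value. For scale only, carrying over the nominal IV ratio (24 / 16 = 1.5) would give 1.5 × 1800 = 2700 mg; the documents do not establish that ratio as an SC safety margin. With overdose defined as a dose above any such limit, a correct SC dose is not an overdose at any weight.

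The cost is a wording change to one bullet. Section 17.1 requires a formal amendment, so it would go into the next one. Dosing, data collection and analysis stay the same.
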